DEVELOPMENT, VALIDATION, AND
EVALUATION OF THE EFFECTIVENESS OF
SIMULATION IN BASIC LIFE SUPPORT TRAINING
(SBLST), ON NEWLY EMPLOYED NURSES IN
GOVERNMENTAL JORDANIAN HOSPITALS

Study Protocol

Last update On 20-4-2023

Malaysian Human subjects protection review board date: 20-4-2023

Study title:
DEVELOPMENT, VALIDATION, AND EVALUATION OF THE
EFFECTIVENESS OF SIMULATION IN BASIC LIFE SUPPORT TRAINING
(SBLST) ON NEWLY EMPLOYED NURSES IN GOVERNMENTAL
JORDANIAN HOSPITALS

Objective

The general objective of this study is to develop, validate and evaluate the effectiveness of simulation in basic life support training (SBLST) among newly employed nurses in Jordanian governmental hospitals; the study design is a basic experimental study design, randomized control trial (RCT) design, the dependant variables measure in this study; knowledge, practice and confidence by using a pre-test and two follow up tests, two groups are participating in this study; experimental and control group. The control group treatment is the standard intervention (brochure), and the experimental group intervention is a simulation in basic life support training (SBLST); researchers' hypothesized that there are no significant differences between the control and experimental group in the inclusion criteria and pre-test score; furthermore, the simulation in basic life support training intervention significantly improves knowledge, practice and confidence level among newly employed nurses (NEN) in Jordanian governmental hospitals; moreover, there is a significant difference between control and experimental group in the post-test scores in all dependant variables. The study process includes four steps

- Perform the pre-test (assess knowledge, practice confidence surveys)
- Education intervention knowledge and practice
- Perform the post-test 1 (assess knowledge, practice confidence surveys)
- Perform post-test 2 (assess knowledge, practice confidence surveys)

Research Hypotheses

- i. The simulation in basic life support training intervention effectively improves knowledge among newly employed nurses (NEN) in Jordanian governmental hospitals.
- ii. The simulation in basic life support training intervention effectively improves practice among newly employed nurses (NEN) in Jordanian governmental hospitals.
- iii. The simulation in basic life support training intervention effectively improves the confidence level among newly employed nurses (NEN) in Jordanian governmental hospitals.

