- iv. There is no significant difference in means between the pre-test among the newly employed nurses (NEN) among interventional and the control groups in all dependent variables.
- v. There is a significant mean difference between PRE-SBLST and all POST-SBLST results among NEN in all dependent variables.

Study Design

The study design was a prospective, longitudinal, single-blind basic experimental design, randomized control trial (RCT) design.

Study Location

The study was carried out in Jordan; Amman and Al-Zarqa City. The accessible population was NEN in five hospitals. The researchers selected three Jordanian hospitals. The selection was according to the capacity, capability of the institution and eligibility criteria. Computer-generated randomization (Random Allocation Software, version 1.0) was applied in blocks to allocate the hospitals by distributing them into two arms. The first arm was the control group; selected from three hospitals; Prince Hamza Hospital, AL-Basheer Hospital, and AL-Zarqa Governmental Hospital (n=51); the second arm was the interventional group from two hospitals; Prince Faisal Governmental Hospital and Dr.Jameel AL-Totanji Hospital.

Randomization of the Hospitals

To prevent data contamination between the control and interventional groups, computer-generated randomization (Random Allocation Software, version 1.0) was applied in blocks to allocate the hospitals by distributing them into two arms. The first arm was the control group; selected from three hospitals; Prince Hamza Hospital, AL-Basheer Hospital, and AL-Zarqa Governmental Hospital (n=51); the second arm was the interventional group from two hospitals; Prince Faisal governmental hospital and Dr.Jameel AL-Totajji hospital. The control and interventional groups were selected from different hospitals because the researchers are always worried about data contamination and try to minimize it between the control and intervention groups; if the sample was selected from the same area and both groups worked closely together, the data would be contaminated.

Inclusion Criteria

The researchers tried to maintain homogeneity and minimize any variations among the participants by

1. selecting both interventional and control groups from newly employed nurses
2. Male and female participants
3. Participants only who understand the questionnaires and interventions in English

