4. Participants who were previously on-seat undergraduate nursing students last two years, 2020 (4th year nursing bachelor level) and 2021 (3rd year nursing bachelor level) in the period of COVID-19 pandemic and receive basic and clinical learning by online method, and now became a newly employed nurse (NEN) in hospitals and delivered care to the patient.
5. Participants can attend five to seven hours of SBLST session.
6. For more control, we selected nurses who rarely face CPR and do not attend BLS raining the last two years.

Exclusion Criteria

1. The researchers excluded the NEN participants working in intensive care units because ICU nurses face CPR and perform BLS daily.
2. Excluded participants with medical or physical health problems (e.g., pregnant women and participants complaining of lower back pain).
3. Participants who attended CPR training less than two years previously were also excluded. Finally,
4. NEN who upgraded their educational degree from a diploma to a bachelor's degree were excluded.

Research Instruments

The study consists of a pre-test, intervention, immediate post-test-1 after the intervention, and finally, the post-test-2 three months after the intervention. This study measured knowledge, practice, and confidence through pre- and post-tests in control and experimental groups. This study used two interventions: SBLST for the interventional group and AHA-BLS 2020 brochure as a standard treatment for the control group. Data collection proceeded using the Google Form Platform (A web-based instrument Copyrighted by Google application).

The evaluation process includes a pre-test and two follow-up assessments to measure knowledge, practice and confidence. The researcher will analyse the means of each test; the total dependent variables were 30 questions listed in.

Languages of the Tools

According to the HCP educational level, all four sections of the tools assessment are written in English; furthermore, the researchers' assistance clarified any misunderstanding points or need for translation to the participants.

Tools Sections

The tools consist of five sections; research information sheet and consent forms, demographical data, knowledge assessment tools, skills assessment tools, and confidence level assessment tools.

Research information sheet and Consent Forms

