Adult half-body manikin and a pediatric full-body manikin are necessary; with lung bag inflation and deflation characteristics, palpable carotid pulse, the chest includes spring inside to facilitate chest recoil, and chest compression board, bag-valve-mask-ventilation, chest compression performed on the Charlie simulator to relieve choking. The principles investigator (PI) had a master's degree in critical care nursing, eighteen years of experience between ICUs, lecturers and clinical instructors, valid BLS and ACLS, training of trainers in nursing education, and randomized control trial training. The facilitator must have CPR certifications in BLS and ACLS, enough expertise in education and training, and good communication skills the investigator had a master degree in critical care. Two research assistants supported the

PI in collecting data; one research assistant for the control group and the other for the interventional group.

Post-test

All participants completed the immediate post-test-1 after the interventions. The post-test-2 was conducted by providing the participants with a Google Form Platform link through their phone and email addresses. The post-test after three months evaluates whether the participants' level stayed at the same level or minimized by comparing the mean value between all post-tests. Forty-eight participants in the experimental group completed post-test-2 with a response rate of 94%, and 45 participants in the control group with a response rate of 88%.

Sample Size Estimation

Sample size calculation is performed by using G*POWER software (version 3.1); sample size calculation is summarized and consists of the following steps (1) Select the test family (F-test family), (2) Select the statistical test (Select ANOVA-repeated test, between factors), the preliminary test analysis the researchers used in this study, the rationale for using the Select ANOVA-repeated test between factors due to measure many dependent variables means at different time points. (3) The parameters selected to calculate sample size include one side tail, alpha (α) and equals (0.05)- type one error, Power (P) and equal (0.8), effect size, the number of groups is two (each group = $n/2$) n = the estimated sample size, number of measurements were four measurements (Pre-test, Post-test immediately, Post-test after two months, and Post-test after three months).

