DEVELOPMENT, VALIDATION, AND
EVALUATION OF THE EFFECTIVENESS OF
SIMULATION IN BASIC LIFE SUPPORT TRAINING
(SBLST) ON NEWLY EMPLOYED NURSES IN
GOVERNMENTAL JORDANIAN HOSPITALS

Statistical Analysis Plan

Last update On 20-4-2023

Malaysian Human subjects protection review board date: 20-4-2023

Statistical Analysis Plan

Introduction

The data will be collected through the Google Forms platform, and the researchers will extract the data responses from Google Forms as an Excel sheet (Microsoft Office 2016); all the quantitative data will be coded and transferred to IBM SPSS version 27; the data will be analyzed by using (1) descriptive and (2) inferential statistic.

1. Descriptive Statistics

The descriptive statistic will illustrate the homogeneity and characteristics of NEN in the control and experimental group, including the number and percentage of participants for each group. Also, it will be used to describe statistics for participants' knowledge, practice and confidence level mean percentage in the pre-test and post-test scores.

2. Inferential Statistics

A. Independent T-test

Independent T-test will be used to identify the homogeneity or heterogeneity between pre-tests and post-tests in the control and experimental groups in all dependent variables by interpreting the *P*-value and comparing means (SD). The researchers plan to use independent T-tests despite the normality assumption not being fulfilled depending on the central limit theorem, which states that if samples are more than 30 participants in each group, the researcher can use mean and SD.

B. Repeated Measures-ANOVA

The researchers will use "Repeated Measurement ANOVA" for inferential statistics of the mean of the dependent variables between the interventional and comparator groups in all pre-test and post-tests. Finally, the researchers compared the

*

“Mean,” “Standard Deviation,” and significant level (*P*-value) between tests to explore the effectiveness of the intervention SBLST.

In this step of the analysis, the researchers want to estimate a good idea about the outcomes and how SBLST is considered a good intervention or not after comparing the knowledge score, practice score, and confidence level in both interventional and control groups. The researchers selected a *P*-value < 0.05 for statistical analysis significant to accept the alternative hypothesis or reject the null hypothesis.

C. Effect Size (Cohen’s Score)

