The researchers will calculate the effect size between pre-test and post-test-2 in each group and identify the most effective treatment method that increases knowledge, practice and confidence score. Effect size reflects the SBLST's effectiveness if it produces a small, moderate or large effect. The researchers plan to use Cohen’s formula (d) to calculate the effect size; effect size assists the researcher in interpreting the effectiveness of the SBLST before and after intervention and also interpret the two intervention in two groups after the intervention, according to the following category (<0.2), small effect; (0.2-0.8), moderate effect, (>0.8), large effect; and finally more than 0.9, very large effect (La Cerra et al., 2019).

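### SAP 2.B treats the pre-test as an outcome, plans no pre-test covariate and names no deciding test; the sample size's 80% power belongs to a group main effect that is diluted if the groups start equal

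*SAP*

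**What the plan says.** SAP 2.B applies repeated measures ANOVA "for inferential statistics of the mean of the dependent variables between the interventional and comparator groups in all pre-test and post-tests", followed by a comparison of means, SDs and P-values between tests at P < 0.05. It lists no covariate and does not pick out a model term or an occasion.

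Two other analyses stand beside it, unranked:

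- SAP 2.A: "Independent T-test will be used to identify the homogeneity or heterogeneity between pre-tests and post-tests in the control and experimental groups", read from the P-value and the means.
- SAP 2.C: "The researchers will calculate the effect size between pre-test and post-test-2 in each group and identify the most effective treatment method".

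In the protocol, the Objective expects that "there is a significant difference between control and experimental group in the post-test scores in all dependant variables". Hypothesis iv reads: "There is no significant difference in means between the pre-test among the newly employed nurses (NEN) among interventional and the control groups". Hypothesis v concerns change from pre-test to the post-tests. Research Instruments gives three occasions: the pre-test, then an "immediate post-test-1 after the intervention, and finally, the post-test-2 three months after the intervention".

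Sample Size Estimation selects the between-factors repeated measures ANOVA with four measurements, the first being the pre-test. It gives "the rationale for using the Select ANOVA-repeated test between factors due to measure many dependent variables means at different time points". Alpha is 0.05, power 0.8 and f = 0.26, the last derived from a previous study's post-test results. The result is 72, raised to 102 for dropout. It also says "The parameters selected to calculate sample size include one side tail"; the SAP gives no side.

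**The concern.** The between-factors test compares the two groups on the average of all occasions. An effect that can appear only after training contributes nothing at pre-test, so including that occasion shrinks the averaged difference by one quarter over four occasions, or by one third over three. The sizing puts in a post-test difference as if it applied at every occasion.

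The plan also leaves at least three tests open for each of three outcomes. They answer different questions and have different power, so the 80% figure is tied to no named deciding test, and the test could be chosen after the results are seen. Meanwhile the pre-test score, which every nurse provides, is not used to sharpen the comparison.

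**Working it through.** **Inputs.** From Sample Size Estimation: f = 0.26 (so d = 2 × 0.26 = 0.52 SD), alpha 0.05, four occasions, N = 72, 102 enrolled. From Post-test: 48 and 45 completed post-test-2, N = 93. From Research Instruments: three occasions. Assumed: equal SDs, one common correlation rho between occasions (0.5, range 0.3 to 0.7), the full effect at each post-test unless stated, and no clustering. Tests are two-sided 5% unless stated. Let h = n1·n2/N, which is 18 for 36/36 and 23.226 for 48/45.

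**1. The plan's own figure.** For the group main effect over m occasions with differences e, lambda = h·mean(e)² / [(1+(m−1)rho)/m], with 1 and N−2 df.

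- With 0.52 at all four occasions: lambda = 18 × 0.2704/0.625 = 7.788, power 78.6%.
- With f = (26.64 − 25.03)/(2 × 3.04) = 0.2648, which prints as 0.26 if cut off, power is 80% and N = 72 is reproduced exactly.

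So 72 is the answer for rho about 0.5 with the full difference at every occasion, pre-test included.

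**2. No difference at pre-test, rho 0.5.**

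| Occasions | N | mean(e) | lambda | Power |
|---|---|---|---|---|
| 4 | 72 | 0.390 | 18 × 0.1521/0.625 = 4.380 | 54% |
| 3 | 72 | 0.347 | 18 × 0.1202/0.667 = 3.245 | 43% |
| 3 | 93 | 0.347 | 23.226 × 0.1202/0.667 = 4.187 | 53% |

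The last row runs from 62% (rho 0.3) to 46% (rho 0.7); one-sided at rho 0.5 it is 65%.

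**3. How far this depends on rho.** At rho 0.12, four occasions and N = 72, the diluted test has lambda = 18 × 0.1521/0.34 = 8.05 and about 80% power. The undiluted test would then have 96%, so 72 would not be its 80% solution.

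**4. The other planned tests, N = 93.**

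- Interaction: lambda = h·Σ(e − mean e)²/(1−rho) = 23.226 × 0.1803/0.5 = 8.374 on 2 and 182 df, power 73%. It is 58% at rho 0.3, below the main effect's 62%, and 92% at rho 0.7.
- t-test at one post-test: lambda = 23.226 × 0.2704 = 6.280, power 70% (80% one-sided).

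**5. Separating averaging from adjustment, N = 93, rho 0.5.**

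- One post-test, unadjusted: 70%.
- Mean of both post-tests, unadjusted: lambda = 6.280/[(1+rho)/2] = 6.280/0.75 = 8.374, power 82%.
- Mean of both, adjusted for pre-test: lambda = 6.280/[(1+rho)/2 − rho²] = 6.280/0.50 = 12.56, power 94% (at least 91% over the rho range).
- The same if the effect halves by post-test-2: the mean effect is 0.75d, lambda = 12.56 × 0.5625 = 7.065, power 75% (70 to 87%).

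**6. Hospital allocation.** With 93/5, about 19 nurses per hospital, and an assumed ICC of 0.05, the variance inflates by 1 + 18 × 0.05 = 1.9. A test that ignores this uses an effective critical value of 1.96/√1.9 = 1.42, so a nominal 5% becomes about 15%.

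**7. Pre-test check.** With 51 per arm, gaps up to 1.984 × √(2/51) = 0.39 SD are non-significant.

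**The case against.** The strongest reply is that the shortfall depends on one reading. The Objective speaks of post-test scores, hypothesis v of change, and SAP 2.C of pre-test to post-test-2. The between-factors test is named only in the sizing. This stands: a reader might infer that the trial is simply underpowered through dilution, and the documents do not support that, because they never say the main effect decides. What remains is that no test is named and that the stated power was computed for this one.

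Three other inferences also go too far.

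- That 80% always needs a pre-test difference: step 3 shows this fails at low rho, and hypothesis iv says no significant difference, not exactly zero.
- That the interaction or the t-test would rescue the plan: at rho 0.3 the interaction falls below the main effect.
- That pre-test adjustment accounts for the whole gain from 70% to 94%: half of it comes from averaging. A contrast of the mean of both post-tests minus pre-test, within the planned ANOVA, also gives 82% at rho 0.5 (68% at 0.3, 96% at 0.7). Naming the contrast would be enough to pass 80% there; adjustment adds efficiency and holds up better when rho is low.

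It may also be said that post-test-2 response is already reported, so a change now is late. That is fair, and it governs how the change should be documented. It does not remove the need to say which test decides.

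**Conclusion.** The point holds in a conditional form. It is certain from the text that the pre-test is an outcome occasion, that no pre-test covariate is planned and that no deciding test is named. If the group main effect decides and rho is near 0.5, the stated 80% presupposes a pre-test difference. Without one, power is about 54% (four occasions) or 43% (three) at N = 72, and 53% at N = 93 (46 to 62% over rho 0.7 to 0.3). The main assumption is rho, which the documents do not give; the figures also take the effect as 0.52 SD at each post-test and ignore clustering.

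This should be fixed. It concerns what the trial will count as its answer and a cheap loss of efficiency; it is not proof that the completed sample is inadequate. Separately, SAP 2.A's use of a P-value to show homogeneity at pre-test does not work, since a gap of more than a third of an SD can pass unnoticed.

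**What to change.** For each outcome, state in the SAP:

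- The deciding contrast is the group difference in the mean of post-test-1 and post-test-2, adjusted for pre-test score, by ANCOVA or by a mixed model with pre-test, group, time and group-by-time that uses every nurse with at least one post-test. Say whether it is one- or two-sided.
- Post-test-1 and post-test-2 are also reported separately, because the mean mixes immediate and retained learning.
- The planned ANOVA and t-tests are kept as secondary analyses. The change is dated and acknowledged as made after post-test-2 response was known.
- The model accounts for hospital, since five whole hospitals were allocated, or its P-value is labelled as treating nurses as independent. Clustering both lowers power and inflates type I error, and this change does not cure that.
- The 80% is restated as conditional on the named test, the assumed rho and no clustering.
- Baseline is described by means and SDs, and a non-significant pre-test P-value is not read as proof of homogeneity.

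The cost is SAP wording and one SPSS run per outcome, with no new data.

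### SAP 2.B lists the P-value and SD beside the mean as quantities compared between tests and names no group-by-time contrast, so a shift in significance can be taken for an effect of SBLST

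*SAP*

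**What the plan says.** SAP 2.B plans a repeated-measures ANOVA "for inferential statistics of the mean of the dependent variables between the interventional and comparator groups in all pre-test and post-tests". Its closing sentence then lists three things compared: the mean, the SD and the "significant level (*P*-value) between tests to explore the effectiveness of the intervention SBLST". The next paragraph describes "how SBLST is considered a good intervention or not after comparing the knowledge score, practice score, and confidence level in both interventional and control groups", and the threshold follows: "The researchers selected a *P*-value < 0.05 for statistical analysis significant".

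SAP 2.A applies independent t-tests to the pre-tests and post-tests "by interpreting the *P*-value and comparing means (SD". SAP 2.C adds Cohen's d, both from pre-test to post-test-2 within each group and between the groups after the intervention: "Effect size reflects the SBLST's effectiveness if it produces a small, moderate or large effect".

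In the Protocol, hypothesis iv (Research Hypotheses) expects no significant difference between arms at pre-test, and the Objective expects a significant difference at post-test. The Post-test section judges retention at three months on mean values. It also reports the numbers: "Forty-eight participants in the experimental group completed post-test-2 with a response rate of 94%, and 45 participants in the control group".

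Neither document names a group-by-time interaction, a between-arm difference in change, or a confidence interval.

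**The concern.** A P-value mixes the size of a difference with the number tested and with chance. Two P-values on opposite sides of 0.05 do not show that the underlying differences differ, because that comparison has not itself been tested. An SD describes spread and says nothing about effect.

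The plan's parts fit together in a way that invites this mistake. Hypothesis iv predicts a non-significant pre-test, the Objective predicts a significant post-test, SAP 2.A supplies a separate test at each time, and SAP 2.B names the P-value among the things compared between tests. A reader of the results could then cite 'not significant before, significant after' as proof that SBLST works, or 'significant at post-test-1, not at post-test-2' as proof that the effect faded.

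The first pattern matters most where the arms may differ from the start. Five whole hospitals were allocated, three to control and two to SBLST (Protocol, Randomization of the Hospitals), so a standing gap between arms is plausible.

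**Working it through.** **Inputs from the documents.** 51 nurses per arm (Protocol, Sample Size Estimation). At post-test-2, 48 SBLST and 45 control, which reproduces the stated response rates: 48/51 = 94% and 45/51 = 88%. Planned effect size f = 0.26, which for two groups is d = 2 × 0.26 = 0.52. Threshold 0.05.

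**Assumptions, not in the documents.** Nurses are treated as independent. Scores are normal with equal SDs. The correlation between tests is 0.5 unless stated.

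**1. The same difference with fewer nurses.** For an observed standardized difference d, t = d / √(1/n₁ + 1/n₂). With d = 0.40:

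- 51/51: t = 0.40 / 0.198 = 2.02, P = 0.046
- 48/45: t = 0.40 / 0.207 = 1.93, P = 0.057

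The verdict changes although the difference does not. The window is narrow, however: it covers only observed d between about 0.393 and 0.412.

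**2. No treatment effect, same arm gap at pre-test and post-test-1.** Simulated with 51/51 and two-sided t-tests. The direct test is a t-test on each nurse's change.

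| Standing gap (SD) | Pre-test P ≥ 0.05 and post-test-1 P < 0.05 | Direct test of change, P < 0.05 |
|---|---|---|
| 0 | about 4% | about 5% |
| 0.2 | 10% | about 5% |
| 0.3 | about 14% | about 5% |
| 0.4 | 17% | about 5% |

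The direct test is unaffected because a constant gap cancels out of the change.

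**3. Equal true effect at both post-tests.** Simulated with 51/51 at post-test-1 and 48/45 at post-test-2. The share of trials in which the two P-values fall on opposite sides of 0.05 is:

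| True effect (SD) | Share discordant at correlation 0.5 |
|---|---|
| 0.53 (close to the planned 0.52) | about 28% |
| 0.8 | about 4% |
| 1.0 | under 1% |

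At 0.53 SD the share runs from 33% to 22% as the correlation goes from 0.3 to 0.7. Discordance is common when power is moderate and almost disappears when the effect is large.

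**The case against.** The strongest reply is that the sentence describes ordinary reporting: the means, the SDs and the P-value for each comparison, as a repeated-measures ANOVA prints them. The mean comes first in the list and is a valid quantity. The Protocol's Post-test section judges retention on means. The two-group repeated-measures ANOVA contains a group-by-time term, and SAP 2.C adds an effect measure that does not grow with sample size.

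Much of this stands. A reader might infer that the SAP treats a change in P as a change in SBLST's effect, or that P-values are its sole basis. The documents do not support either reading: no such rule is written, and means and Cohen's d are also used. A reader might also expect the SD to shrink as scores approach the maximum, but the documents give no SDs for these tests.

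The figures are also conditional. Step 1 concerns the t-tests of SAP 2.A. A repeated-measures ANOVA restricted to complete cases would use the same nurses at every test, and the SAP is silent on missing data. Step 2 needs a standing gap, and step 3 weakens quickly as the effect grows.

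The reply does not remove the ambiguity. The P-value is among the things compared, and the stated purpose is effectiveness. The group-by-time term is neither named nor tied to a conclusion. Cohen's d is planned within each arm and between arms after the intervention, not as an estimate, with its uncertainty, of how the arm difference changed.

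**Conclusion.** The point holds as an ambiguity that should be closed, not as a stated error of inference. SAP 2.B puts two quantities that do not measure effect on the same footing as one that does, and the hypotheses make a pattern of significance look like the success criterion.

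The size depends on what is true. Under the assumptions above, the before/after pattern arises without any treatment effect in 10% to 17% of trials if a 0.2 to 0.4 SD gap stands between the arms. With no gap it arises in about 4%, which is no worse than the direct test. False signs of a fading or emerging effect between the two post-tests arise in about 28% of trials near the planned effect, and rarely if the effect is 0.8 SD or more. The correlations and the standing gap are assumptions, and correlation among nurses within a hospital is left out.

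**What to change.** In SAP 2.B, remove the P-value and the SD from the quantities compared between tests, and keep SDs as descriptive statistics only. Add text such as:

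*For each outcome we report the SBLST minus control mean difference with its 95% CI at post-test-1 and at post-test-2. Any statement that the arm difference changed between two tests (pre-test to post-test-1, pre-test to post-test-2, or post-test-1 to post-test-2) rests on the group-by-time contrast for those two tests in the same nurses, reported with its estimate and 95% CI. P-values from separate tests are not compared.*

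This costs a few sentences, needs no new data and uses a contrast available from the model already planned. The Protocol already reports post-test-2 completion, so the change should be dated and recorded as made at that stage. The downside for the authors is that patterns of P-values can no longer be cited as evidence.

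### SAP 2.B promises one verdict from three unranked outcomes at an unadjusted 0.05, with no deciding contrast, time point or combining rule

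*SAP*

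**What the plan says.** - **Verdict and criterion (SAP 2.B).** The researchers want to learn "how SBLST is considered a good intervention or not after comparing the knowledge score, practice score, and confidence level" in the two arms. The criterion is P "< 0.05 for statistical analysis significant to accept the alternative hypothesis or reject the null hypothesis". No sidedness, adjustment or ranking is given. Repeated-measures ANOVA is planned over all tests, without saying whether the group or the group-by-time term decides.
- **T-tests (SAP 2.A).** Independent t-tests are to identify "homogeneity or heterogeneity between pre-tests and post-tests in the control and experimental groups", in all dependent variables.
- **Effect size (SAP 2.C).** Cohen's d is the "effect size between pre-test and post-test-2 in each group and identify the most effective treatment method". The section also mentions comparing the two interventions afterwards. It gives size labels but ties none to success.
- **Hypotheses (Protocol).** Hypotheses i-iii give each outcome its own claim. The Objective predicts that "there is a significant difference between control and experimental group in the post-test scores in all dependant variables". Hypothesis v reads "There is a significant mean difference between PRE-SBLST and all POST-SBLST results among NEN in all dependent variables".
- **Sample Size Estimation (Protocol).** The calculation uses repeated-measures ANOVA with the between-factors option, alpha 0.05 and power 0.8, and names no outcome. It adds: "The parameters selected to calculate sample size include one side tail".
- **Post-test (Protocol).** Post-test-2 is meant to show whether the level reached was kept at three months. Completion is already reported: "Forty-eight participants in the experimental group completed post-test-2 with a response rate of 94" per cent, and 45 controls (88%).

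**The concern.** A single verdict needs a rule that turns several results into one answer, and here there is none. Any one outcome, all three, or three separate claims are all compatible with the text. So are either ANOVA term and either post-test. Both the false-positive risk and the power depend on that choice, which could be made after the results are known. For example, a difference on one outcome straight after training could carry a favourable verdict while the three-month results show nothing. The two ANOVA terms also answer different questions: the group term averages in the pre-test, and the interaction has no direction.

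**Working it through.** **1. The plan's own sample size.** Inputs from Sample Size Estimation: f = 0.26, 2 groups, m = 4 measurements, alpha 0.05, power 0.80. The correlation between measurements is not given; I assume 0.5.

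- lambda = N f² m / (1 + (m − 1)rho) = 72 × 0.0676 × 4 / 2.5 = 7.79, with 1 and 70 df. Power is 0.786, so the stated 72 is reproduced to within 2 points of power. It comes out exactly with f = 0.265, or with rho 0.45-0.47.
- 72 / 0.70 = 102.9, against 102 stated.
- This covers one outcome and the group term, with nothing set aside for three outcomes. At alpha 0.05/3 = 0.0167, power at N = 72 is 0.63, and 0.80 needs N = 100 before dropout.

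**2. Dilution in the group term.** The trial as described under Research Instruments has three occasions. An effect d at both post-tests and none at pre-test averages to (0 + d + d)/3 = 2d/3.

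**3. False-positive rates.** With independent outcomes and one test each, 1 − 0.95³ = 14.3%. For correlated data: 10,000 null trials in each of 24 settings, with arms of 51/51 and 48/45, three outcomes, three occasions, time correlation 0.3-0.7, outcome correlation 0-0.8, two-sided 0.05 and no clustering.

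| What may count | Within one outcome | Any of three outcomes |
|---|---|---|
| One ANOVA term | 5% | 9-15% |
| Either ANOVA term | 9-10% | 19-28% |
| Either term, or a between-arm t-test at either post-test | 12-14% | 24-37% |
| One pre-test-adjusted post-test-2 contrast, Holm | – | 3-5% |

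If all three must succeed (adjusted post-test-2 contrast), the rate is at most about 1.5% when all three are null. It is about 2-5% when two outcomes truly improve and one does not; the nominal ceiling is 5%. If one-sided 0.05 is meant, one post-test-2 test per outcome gives 9-15% favouring SBLST across three.

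**4. Power.** d = 2 × 0.26 = 0.52, or (26.64 − 25.03)/2.84 = 0.57 from the means in Sample Size Estimation. With 48/45 completers, the noncentrality is d × √(48 × 45/93) = 4.82d, that is 2.51 to 2.73.

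- Unadjusted post-test contrast: 70-77% at 0.05, and 53-62% at 0.0167 (Holm's first step).
- Adjusted for the pre-test, assumed correlation 0.5 (noncentrality divided by √0.75): 82-88% and 67-76%.
- ANOVA group term at 0.05, effect at both post-tests, time correlation 0.3-0.7: 45-69%. The adjusted post-test-2 contrast gives 74-96%.
- All three outcomes, unadjusted: 0.698³ = 0.34 to 0.770³ = 0.46 if independent, and at most 70-77%.

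**5. What allocation by hospital does to these figures.** Assume 15 nurses in each of 3 control hospitals and 24 in each of 2 SBLST hospitals, and ICC 0.05. The true variance of the arm difference, in units of the total variance, is 0.05/3 + 0.95/45 + 0.05/2 + 0.95/48 = 0.0826. An individual-level analysis assumes 1/45 + 1/48 = 0.0431. The standard error is therefore too small by a factor √1.92 = 1.38, and one nominal 5% test rejects about 16% of the time. With three independent outcomes, Holm would reject at least once in about 24% of null trials. At ICC 0.01 and 0.10 this is about 8% and 40%.

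**The case against.** **The protocol does point to a term.** The between-factors option, and SAP 2.B's wording about means between the arms, lean to the group term. That stands. With that term alone, the rates are 5% per outcome and 9-15% across three. But the SAP does not make it the deciding test, and it is a weak choice for an effect that begins after training.

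**The plan never says that any significant result is enough.** This also stands. A reader might infer that the plan carries a 24-37% false-positive risk. The documents do not support that. It would require one significant result to suffice, either ANOVA term to count, and SAP 2.A to mean between-arm t-tests at both post-tests. The last is only an inference from loose wording.

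**The all-variables wording could be the rule.** The Objective and hypothesis v speak of all dependent variables, which would need no adjustment. But these are predictions standing beside three separate hypotheses; the SAP does not turn them into a success criterion.

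**Choosing post-test-2 is partly preference.** Fair. SAP 2.C applies it to change within each arm, and hypotheses i-iii could be answered at post-test-1. The investigators must confirm the time point.

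**Hospitals matter more.** Agreed. Clustering is the larger problem, and a combining rule does not solve it.

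**Conclusion.** The point holds as a gap in the decision rule, and it should be closed. Its size depends on the reading, and the documents do not select one:

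- **One significant outcome suffices:** about 9-15% with one ANOVA term per outcome. The higher rates need additional tests to count.
- **Hypotheses i-iii are separate claims:** no inflation with one named term (5% each), and about 9-10% each if either term may count.
- **All three must succeed:** at most about 5%, at a cost in power.

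These figures assume normal scores, no clustering and the correlations stated. A reader might also infer that Holm would secure 3-5% in this trial. It would not, because 3 hospitals against 2 were allocated and the figure ignores that.

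**What to change.** In SAP 2.B:

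1. For each of hypotheses i-iii, name one deciding contrast: SBLST minus brochure at one named post-test, adjusted for the pre-test score. Post-test-2 is suggested because it answers the protocol's three-month question; the investigators should confirm it.
2. State sidedness, and reconcile it with the one-tail wording in Sample Size Estimation.
3. State one combining rule: Holm across the three outcomes at overall two-sided 0.05, or all three significant at two-sided 0.05.
4. Label the other t-tests, ANOVA terms and Cohen's d grades as supportive for the verdict. Hypothesis v may still be reported as its own within-arm comparison.
5. Date the change. Post-test-2 completion is already reported, so call it post hoc if arm comparisons have been seen. In that case it improves transparency but does not restore prespecified error control.

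The cost is a few sentences and no new data, plus power. Without clustering, unadjusted power per outcome falls from about 70-77% to 53-62% at Holm's first step; pre-test adjustment recovers part of it. Requiring all three costs more if the outcomes are weakly correlated.

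Hospital allocation needs its own decision. Hospital cannot simply be added as a fixed covariate, because it is aliased with arm: intercept, arm and four hospital indicators make six columns of rank 5. A t-test on hospital means has 3 df. With the assumed hospital sizes, d 0.52-0.57, no pre-test adjustment and ICC 0-0.10, its power is only about 18-43% at 0.05 and 7-19% at 0.0167.
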